- n. The Early Treatment Termination (ETT) Visit should occur for any subject who discontinues ofatumumab treatment prior to Cycle 7 Day 1. ETT assessments need not be performed for those assessments performed within the previous 2 weeks (previous 30 days for Disease Response Assessments [see [Table 5](#)] and the QoL assessment).
- o. The clinical visit schedule should be maintained until Cycle 9 for subjects who discontinue study treatment prior to Cycle 9 for reasons other than PD. The clinical assessment period then begins at Cycle 9, with visits occurring every other month until disease progression, subject withdrawal, or initiation of additional anticancer therapy; no additional study drug (ofatumumab) will be administered.

Table 5: Disease Response & Follow-up Assessments for All Subjects

Assessments ^d	Screening (baseline)	Cycle 3 Day 1	Cycles 5, 7, 11, 15, & 19 Day 1	Early Termination from Study Treatment (ETT) ^a ≤7 days of last dose	Disease Follow-up ^b Every 6 months (±4 weeks)	Survival Follow-up ^c Every 6 months (± 4 weeks)
CT scans of chest, abdomen and pelvis ^e	X	X	X	X	X	
Bone marrow biopsy and/or bone marrow aspiration ^f	X	X	X	X	X	
Complete blood count (CBC) and differential count ^g	X	X	X	X	X ⁱ	
Blood sample for assessment for minimum residual disease (MRD) ^h		X	X	X	X	
Focused physical examination ^g , disease related constitutional symptoms assessment, and ECOG performance status	X	X	X	X	X	
Survival						X

- a. ETT Disease Response Assessment is not necessary if a Disease Response Assessment was performed within the previous 30 days. In the absence of disease progression or initiation of subsequent anticancer therapy, all subjects with ETT prior to Cycle 19 Day 1 will maintain the disease response assessment schedule (Cycles 5, 7, 11, 15, & 19)
- b. All subjects with no disease progression by Cycle 19 Day 1 will continue Disease Response Assessments (Section 6.5.3.1) every 6 months until disease progression, subject withdrawal, or initiation of additional anticancer therapy. The first disease follow-up assessment after Cycle 19 Day 1 should occur approximately 6 months after last disease assessment.
- c. All subjects will have Survival Follow-up for up to 6 years after randomization or until death. This assessment can be conducted by telephone interview. Information on initiation of other anticancer therapy (including start date, therapy type, and response on treatment) will also be collected.

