Administration of ofatumumab will not exceed the 12 doses (within 7 cycles) as described in the prescribing information. After dosing with ofatumumab is complete (ie, through Cycle 7 or ETT), subjects will continue to have clinical assessments every odd cycle (Clinical Assessment Period) through Cycle 19 Day 1 or until disease progression, subject withdrawal, or initiation of additional anticancer treatment. After Cycle 19 Day 1, disease response assessments will continue every 6 cycles until disease progression, subject withdrawal, or initiation of additional anticancer treatment.

If a subject initiates another anticancer therapy following treatment with ofatumumab, then the subject will be discontinued from the Clinical Assessment Period and will be followed for survival as described in [Table 5](#).

Subjects who have documentation of PD confirmed centrally at any time during the study may be eligible to receive the opposite study medication as part of a separate Verastem-sponsored extension protocol (Study IPI-145-12). Additional extension protocol eligibility criteria must also be met.

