6.3.9 Disease Response Assessments

Response and progression will be measured by the following assessments as indicated in [Table 5](#):

- Bone marrow aspirate and/or bone marrow biopsy

- CT scans of chest, abdomen and pelvis (See [Section 6.3.9.1](#))
- CBC and differential count
- Blood sample for assessment of MRD in subjects with documented CR or CRi
- Disease-Related symptoms
 - Focused Physical exam
 - ECOG performance status as a measure of fatigue
 - Disease-related constitutional symptoms (fever [ie, temperature >38°C/100.5°F] without evidence of infection, weight loss, and drenching night sweats without evidence of infection)

These evaluations will be done until PD is documented or other anticancer therapy is initiated (at which point the subject will enter the Survival Follow-up Period), or death occurs.

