6.4 EARLY TREATMENT TERMINATION OF DUVELISIB OR OFATUMUMAB

If at any time during treatment with study drug (duvelisib or ofatumumab) a subject has an AE resulting in permanent discontinuation of study treatment, PD, initiates new anticancer therapy, or withdraws consent, then the assessments outlined below will be performed within 7 days of study treatment discontinuation or the decision to discontinue study treatment. ETT assessments include:

If performed within previous 14 days, do not need to be repeated:

- Urine or serum pregnancy tests will be collected from all women of childbearing potential (WCBP)
- Concomitant Medications and Procedures collection
- AE and SAE assessment
- Blood chemistry
- Liver function tests
- Biomarker assessments

If performed within previous 30 days, do not need to be repeated:

- Disease response assessments:
 - Focused physical exam /constitutional symptoms
 - Bone marrow biopsy/aspirate (if indicated)
 - Hematology
 - Blood sample for MRD
 - ECOG
 - CT scan
 - Quality of life (QoL) EQ-5D and FACIT-F

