### 3.5.2 Planned Analyses for OS

There will be three planned analyses for OS: two interim analyses and one final analysis. The first interim analysis of OS will be performed at the time of the planned PFS interim analysis after 93 PFS events have occurred. The estimated number of OS events at this first OS interim analysis is 24. The second interim analysis of OS will be performed at the planned PFS final analysis, after 185 PFS events have occurred. If the planned final analysis of PFS is not performed due to an early stop for efficacy, then the second interim analysis of OS will be conducted approximately 1 year after the first interim OS analysis. The estimated number of OS events at the second OS interim analysis is 58. The final analysis of OS will take place after the completion of follow-up for all subjects. The estimated number of OS events at the final OS analysis is 161. The information fractions at the two interim OS analyses and the final OS analysis will be calculated based on 161 planned OS events at the final OS analysis. The cumulative alpha spending at the three analyses will be 0.0001, 0.0249, and 0.0250, respectively. If the OS analyses occur at 24, 58, and 161 OS events, the p-value stopping boundaries for the three analyses will be 0.0001, 0.0249 and 0.0003, respectively. The actual p-value stopping boundaries will be derived from the actual number of OS events that occurred. The statistical

significance of OS will be claimed based on the hierarchical testing procedure as specified in [Section 6.3](#).

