#### 7.2.2.2 Overall Survival (OS)

The primary analyses of OS will be based on the ITT analysis set.

Subjects without documentation of death at the time of the data cutoff for analysis will be censored at the date the subject was last known to be alive, or the data cutoff date, whichever is earlier. A stratified one-sided log-rank test will be used to compare OS between the 2 treatment groups. The HR along with the 95% CI will be estimated using a stratified Cox model. For both the stratified log-rank test and the stratified Cox model, the strata will be those used for stratified randomization, with potential pooling of strata specified earlier in [Section 7.2](#). A Kaplan-Meier plot for OS will be presented by treatment group. Estimates and 95% confidence intervals for the

25th percentile, median, and 75th percentile for OS will be presented by treatment group (if estimable). Probabilities of survival at selected time points may also be presented.

A majority of subjects can be expected to take subsequent anticancer therapy, especially after disease progression. To adjust for the effects of subsequent therapy, the following sensitivity analysis may be performed: Primary analyses except additional censoring at the start date of subsequent therapy

Subgroup analyses for OS will be performed using the subgroups specified in [section 6.5](#). The HR (duvelisib /ofatumumab) with its 95% CI will be calculated based on an unstratified Cox regression model for each subgroup. The HRs and their 95% CIs will be displayed for all subgroups graphically in a forest plot.

**OS follow-up time**, defined as time from randomization to the date of last procedure or assessment (including telephone interview), will be summarized by treatment arm and for the two treatment arms combined (total) using the reverse Kaplan-Meier method, which applies Kaplan-Meier method to the OS data with the same event/censoring time as the primary OS analyses while reversing event/censoring indicator. The 25th percentile, median, and 75th percentile of OS follow-up time will be presented.

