#### 7.2.2.2 Overall Survival (OS)

The primary analyses of OS will be based on the ITT analysis set.

Subjects without documentation of death at the time of the data cutoff for analysis will be censored at the date the subject was last known to be alive, or the data cutoff date, whichever is earlier. A stratified one-sided log-rank test will be used to compare OS between the 2 treatment groups. The HR along with the 95% CI will be estimated using a stratified Cox model. For both the stratified log-rank test and the stratified Cox model, the strata will be those used for stratified randomization, with potential pooling of strata specified earlier in [Section 7.2](#). A Kaplan-Meier plot for OS will be presented by treatment group. Estimates and 95% confidence intervals for the

25th percentile, median, and 75th percentile for OS will be presented by treatment group (if estimable). Probabilities of survival at selected time points may also be presented.

A majority of subjects can be expected to take subsequent anticancer therapy, especially after disease progression. To adjust for the effects of subsequent therapy, the following sensitivity analysis may be performed:

1. Primary analyses except additional censoring at the start date of subsequent therapy
2. Rank preserving structural failure time (RPSFT) analysis
3. Inverse probability of censoring weighted (IPCW) analysis

The following sensitivity analyses will be performed:

- Analysis using the PP analysis set.
- Analysis using the AT analysis set.
- Unstratified analyses: An unstratified log-rank test (one-sided) will be used to compare the two treatment arms. An unstratified Cox regression (one-sided) will be used to estimate the hazard ratio (duvelisib /ofatumumab) with its 95% confidence interval.

Subgroup analyses for OS will be performed using the subgroups specified in [section 6.5](#). The HR (duvelisib /ofatumumab) with its 95% CI will be calculated based on an unstratified Cox regression model for each subgroup. The HRs and their 95% CIs will be displayed for all subgroups graphically in a forest plot.

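### Does the SAP need a mandatory IPCW analysis of overall survival because its only adjustment for later therapy censors at therapy start?

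*SAP*

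**What the plan says.** SAP V4.0 section 7.2.2.2 makes the ITT stratified log-rank test and Cox model primary for OS. It then states: "A majority of subjects can be expected to take subsequent anticancer therapy, especially after disease progression". To deal with this it names one supportive analysis, which may or may not be run: "Primary analyses except additional censoring at the start date of subsequent therapy". No weighted or structural method appears in any V4.0 analysis section. The abbreviations and reference list still carry such methods. The superseded V3.0 listed "Inverse probability of censoring weighted (IPCW) analysis" among its optional adjustments, which is context only.

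Section 3.5.2 states the OS boundaries conditionally: "If the OS analyses occur at 24, 58, and 161 OS events", they are 0.0001, 0.0249 and 0.0003. Section 3.2 gives median PFS of 9 months (ofatumumab) and 15 months (duvelisib).

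Protocol section 4.1 says subjects with centrally confirmed progression "may be eligible to receive the opposite study medication" in an extension study. Table 5, footnote c, covers later therapy: "Information on initiation of other anticancer therapy (including start date, therapy type, and response on treatment) will also be collected". Section 6.3.9 limits disease evaluations: "These evaluations will be done until PD is documented or other anticancer therapy is initiated". Section 6.4 sets an early-termination (ETT) visit for events during study treatment: "PD, initiates new anticancer therapy, or withdraws consent, then the assessments outlined below will be performed within 7 days of study treatment discontinuation".

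**The concern.** Censoring at therapy start is unbiased only if those who start therapy have the same outlook as comparable subjects who do not. The SAP itself ties later therapy to progression. Progression is prognostic, is expected earlier on ofatumumab, and opens crossover in both directions. Subjects would therefore be removed selectively, at times that differ by arm.

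OS is a key secondary endpoint. If the analysis were run, its hazard ratio could sit near the ITT value or move away from it because of who switches, and nothing else planned for OS would show which. IPCW is a recognised method for this problem, and therapy start dates are collected, so requiring it looks like an inexpensive improvement.

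**Working it through.** **1. The plan's own figures.** Schoenfeld power for PFS, with z = 1.960 for one-sided 0.025, is Φ(√(185/4) × |ln 0.6| − 1.960) = Φ(6.801 × 0.5108 − 1.960) = Φ(1.514) = 93.5%. The plan says about 93%. The OS cumulative spends 0.0001, 0.0249 and 0.0250 at 24, 58 and 161 deaths give nominal levels 0.0001, 0.0249 and 0.00027, as stated after rounding. None of these depends on any adjustment for later therapy.

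**2. How far can simple censoring move the hazard ratio?** Simulation 1 takes the PFS medians, accrual and dropout from the plan. Death hazards and switching rates are assumed. Switching has no effect on death, so the ITT hazard ratio is the truth. Switching is the percentage of progressors on ofatumumab/duvelisib.

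| Model (deaths; SAP 24/58/161) | ITT | 70/70 | 80/60 | 60/80 |
|---|---|---|---|---|
| C: hazard rises 1.25-fold at progression (23/55/164) | 0.96 | 0.96 | 0.98 | 0.93 |
| B: 2-fold rise plus frailty (24/59/159) | 0.93 | 0.92 | 1.08 | 0.80 |
| A: not fitted to SAP deaths (17/50/182) | 0.86 | 0.80 | 0.92 | 0.71 |

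In these and two further patterns (80/80 and a 10-point gap either way), 51-65% of subjects switch by the final analysis and 45-65% of deaths are discarded. In the two models fitted to the SAP's deaths, equal uptake gives almost no shift; larger shifts need unequal uptake. A fitness marker (30% of progressors, 2.5-fold post-progression hazard) that affects switching alike in both arms moves C from 0.98 to 0.96 and B from 0.93 to 0.91. If it acts on ofatumumab only, C moves to 0.87 and B to 0.84.

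At 27.5 months 33-43% have switched. Simple censoring then discards 23-44% of deaths, leaving 58 × 0.56 ≈ 32 to 58 × 0.77 ≈ 45.

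**3. Does IPCW repair it?**
- *Simulation 1, trials of 300.* With the marker in the weight model, the mean hazard ratio was within about 0.012 of ITT at the final analysis and 0.03 at 27.5 months. With the ofatumumab-only marker left out, IPCW gave 0.81 in both C and B. Simple censoring gave 0.87 and 0.85; the truth was 0.98 and 0.94.
- *Simulation 2, different assumptions.* Pre-progression death hazard is 0.004 per month; therapy starts at 0.05 per month after progression. Truth / simple / IPCW on progression status: 2-fold rise 0.936/0.890/0.925; 4-fold 0.871/0.805/0.862; 6-fold 0.839/0.762/0.837. IPCW helps here.
- *Simulation 2, uptake 0.10 per month, stabilised weights.* At 4-fold: 0.875/0.793/0.833, so IPCW closes (0.833 − 0.793)/(0.875 − 0.793) = 49% of the gap. With a post-progression decline marker: truth 0.825, simple 0.808, IPCW on progression 0.820, IPCW on progression plus marker 0.750. At the lower uptake the marker run gave 0.818, 0.780, 0.830 and 0.824.

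**4. What would the weights be built on?** Progression is normally found at an assessment that includes ECOG and blood counts, so values at progression will usually exist. Nothing further is scheduled between progression and the next therapy. Survival follow-up is six-monthly and may be by telephone. The ETT visit does not fill the gap evenly. On ofatumumab it applies before Cycle 7 Day 1: 21 + 5 × 28 = 161 days, or 161/30.44 = 5.3 months. The planned proportion still event-free is then 2^(−5.29/9) = 0.665. On duvelisib it applies before Cycle 19 Day 1: 21 + 17 × 28 = 497 days, or 16.3 months, with 2^(−16.33/15) = 0.470 event-free. At most about 33% of ofatumumab subjects and 53% of duvelisib subjects have a PFS event inside the window.

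**5. Precision, trials of 300 (SD of the log hazard ratio).** Final analysis: ITT 0.15-0.17, simple censoring 0.22-0.24, IPCW 0.24-0.28. At 27.5 months: 0.26-0.30, 0.31-0.38 and 0.37-0.48. As 95% limits, exp(1.96 × SD), IPCW spans a factor of 1.60-1.73 at the final analysis and 2.1-2.6 at 27.5 months. The largest tabulated shift is a factor of 0.86/0.71 = 1.21.

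**The case for a change.** The strongest case for a change is consistency. For PFS, where new therapy is also censored, the SAP commits to event-free survival as an alternative and lists seven sensitivity analyses. ORR has eight. OS, also a key secondary endpoint, has no committed one, although subsequent therapy is expected in most subjects. Both simulations contain settings in which simple censoring is wrong by 0.05 or more and IPCW is nearly right. No new data collection is needed. A label and counts of switchers by arm would cost almost nothing.

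Part of this stands. The censoring is potentially informative, and a report that shows it should say so. The rest does not make a correction. The PFS censoring rule is part of the primary analysis, so an alternative there tests the confirmatory result; the OS censoring touches only an optional supportive one. IPCW does well when the drivers of switching are measured and modelled, and the schedule gives limited grounds to assume that. If the two adjusted results differed, a reader still could not separate selective switching from a failed weight model. As for counts, SAP section 6.1 already asks for events and censored subjects, by treatment group, in every time-to-event analysis. Deaths dropped in each arm follow by subtraction from the ITT table, and starters of later therapy can be tabulated from the dates collected.

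**Conclusion.** No change follows. The observation is correct: the only named adjustment is optional and may be informative. The error could be negligible or about 0.15 on the hazard ratio, in either direction, and the documents do not give the hazards or switching rates that would settle it. It affects no alpha, boundary, event count or confirmatory conclusion, because OS is tested by ITT.

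Making IPCW mandatory would exchange one untestable assumption for another, with less precision. It was better in some plausible settings and worse in others. Leaving it out is a fair trade-off for the sponsor to make. A caution beside the censored result is ordinary reporting practice and alters no rule or number. The unused IPCW and RPSFT entries in the abbreviations and references, and the lack of a section 8 entry for V4.0, are clerical.

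This rests on assumed death hazards, on switching within months of progression, and on switching having no effect on death. The simulations therefore measure selection bias only, not how well any method removes a real effect of later therapy.

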#### 7.2.2.3 *Lymph Node Response Rate*

The primary analyses of lymph node response rate will be based on IRC assessment in the ITT analysis set. The number of subjects with lymph node response, estimated lymph node response rate, and a 2-sided 95% CI will be provided for each treatment arm.

Lymph node response rate will be analyzed using the CMH test (one-sided) to compare the two treatment groups. The strata for the test will be those used for stratified randomization, with potential pooling of strata specified earlier in [Section 7.2](#).

A sensitivity analysis will be performed using lymph node response rate based on investigator measurements.

#### 7.2.2.4 *Hematologic Improvement Rate*

A subject with a hematologic improvement is one who consistently met the criteria of an improvement in neutrophil count, hemoglobin or platelet count for a period of at least 60 days during which the subject did not have a transfusion or exogenous cytokines. Missing data or missing scheduled assessments during a potential 60-day hematologic improvement episode will result in categorization of not having a hematologic improvement.

The number of subjects with hematologic improvement, estimated hematologic improvement rate, and a 2-sided 95% CI will be provided for each treatment arm.

Hematologic improvement rate will be compared between treatment groups using one-sided CMH test. The strata for the test will be those used for stratified randomization, with potential pooling of strata specified earlier in [Section 7.2](#).

#### 7.2.2.5 *Duration of Response (DOR)*

DOR will be presented using the Kaplan-Meier method for each treatment arm based on all randomized subjects with a documentation of response (i.e., CR, CRi, PR, or PRwL) as determined by IRC assessment. The censoring method will be the same as that for the primary endpoint (see [Appendix A](#)). The Kaplan-Meier plot for DOR will be presented by treatment group. Estimates and 95% confidence intervals for the 25th percentile, median, and 75th percentile for DOR will be presented by treatment group (if estimable). No treatment comparison will be performed.

### 7.2.3 **Analyses of Exploratory Efficacy Endpoints**

#### 7.2.3.1 *Improvement in Disease-Related Symptoms*

Disease-related symptoms of fever, weight loss, and drenching night sweats will be assessed as present or absent at each timepoint. Improvement in each of the three disease-related symptoms from baseline will be analyzed separately. The summary will display by treatment arm the proportion of subjects with an improvement while on treatment. Descriptive analysis of improvement in these disease-related symptoms will also be presented over the course of the study (eg, for each scheduled assessment) by treatment arm.

The disease-related symptom of fatigue will be measured by the ECOG performance status. Summary statistics will be provided by treatment arm for the ECOG score and the change from baseline at each timepoint.

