4.1 SCHEDULE OF ADMINISTRATION

Subjects who meet all the eligibility criteria at Screening will return to the clinic on Day 1 to receive their first dose of study drug (either duvelisib or ofatumumab). The first treatment cycle for each treatment arm will be 3 weeks (21±2 days). Subsequent treatment cycles will be 4 weeks (28±4 days).

Arm 1 (Duvelisib): Subjects randomized to duvelisib will receive their first dose of study drug in clinic on Day 1, initiating Cycle 1 of treatment. These subjects will return for a second clinical visit on Day 8±2. Cycle 1 will be 21 days, with all subsequent cycles 28 days in length. Cycle 2 will have clinic visits on Day 1 and on Day 15±2. Each subsequent cycle (Cycle 3-7) and then every odd cycle (Cycle 9 to 19) will have only one clinic visit on Day 1. Subjects will receive duvelisib continuously for 18 cycles or until disease progression or unacceptable toxicity, whichever comes first. After completing approximately 18 cycles of treatment with duvelisib, subjects who, in the judgment of the investigator, may derive benefit from continued treatment may receive additional cycles of duvelisib until disease progression or unacceptable toxicity. However, to receive additional cycles of duvelisib beyond 18 cycles, subjects must have CLL/SLL requiring treatment by Cycle 19 Day 1 (Reference 4.2.1.2). Subjects who receive duvelisib beyond 18 cycles (Cycle 19 Day 1) will maintain clinical visits every odd cycle (Cycle 21, 23, etc) until disease progression, subject withdrawal, or initiation of additional anticancer treatment. After Cycle 18, disease response assessments will continue every 6 cycles for those subjects who have not had disease progression, withdrawn consent, or initiated additional anticancer treatment.

Arm 2 (Ofatumumab): Subjects randomized to ofatumumab will receive IV treatment according to the approved prescribing information.^{10, 11} Subjects will receive 8 weekly IV infusions, starting with an initial dose of ofatumumab of 300 mg followed by seven weekly doses of 2000 mg. Thereafter, subjects will receive 2000 mg ofatumumab once every cycle for four cycles or until disease progression or unacceptable toxicity, whichever comes first.

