### 3 STUDY DESIGN

#### 3.1 Overview

Study IPI-145-07 is a two-arm, randomized (1:1 ratio), open-label, phase 3, superiority trial designed to evaluate the efficacy and safety of duvelisib compared to ofatumumab.

Subjects who meet all the eligibility criteria at Screening will return to the clinic on Day 1 to receive their first dose of study drug (randomized to either duvelisib or ofatumumab). The first treatment cycle for each treatment arm will be 3 weeks (21±2 days). Subsequent treatment cycles will be 4 weeks (28±4 days).

Subjects randomized to duvelisib will be given a starting dose of 25 mg duvelisib administered orally twice daily (BID) initially in a 21-day treatment cycle followed by 28-day treatment cycles for up to 18 cycles or until disease progression or unacceptable toxicity (whichever comes first). After completing approximately 18 cycles of treatment, subjects who, in the opinion of the investigator, may derive benefit from continued treatment may receive additional cycles of duvelisib until disease progression or unacceptable toxicity. Subjects randomized to ofatumumab will receive treatment consistent with the approved product labeling: 8 weekly infusions, starting with an initial IV dose of 300 mg ofatumumab on Day 1 followed by seven weekly doses of 2000 mg. Thereafter, subjects will receive 2000 mg ofatumumab once every month for four months or until disease progression or unacceptable toxicity (whichever comes first), as outlined in the schedule of assessments. Administration of ofatumumab will not exceed the 12 doses (within 7 cycles) as described in the prescribing information.

Subjects will be followed for survival for up to 6 years (or other duration as specified by the protocol) from randomization or until death. Follow-up visits will occur every 6 months which can be conducted through a telephone interview.

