### 5.3 Exploratory Endpoints

The exploratory efficacy endpoints of the study are:

- Improvement in disease-related symptoms of fatigue, weight loss, unexplained fevers and night sweats from Baseline
- Minimal Residual Disease (MRD) in subjects with documented CR or CRi
- Time to Response (TTR), defined as the time from randomization to the first documentation of response (CR, CRi, PR or PRwL)

The QoL endpoints of the study are:

- Health-related QoL of subjects as assessed by the following subject-reported questionnaires:
  - EuroQol-5D (EQ-5D)
  - Functional Assessment of Chronic Illness Therapy-Fatigue (FACIT-F)

The biomarkers of the study are:

- Serum and tissue biomarkers and blood immunophenotype
- Tumor genomic features (eg, DNA sequence variation, DNA copy number variation, and/or RNA expression)
- Germline DNA sequence variations

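### SAP 7.2.3.1: the on-treatment proportion for symptom improvement gives duvelisib up to about twice as many scheduled looks as ofatumumab

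*SAP*

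**What the plan says.** The relevant text is in SAP V4.0, section 7.2.3.1. "Disease-related symptoms of fever, weight loss, and drenching night sweats will be assessed as present or absent at each timepoint". Each of the three symptoms is analysed separately, and then: "The summary will display by treatment arm the proportion of subjects with an improvement while on treatment". The section does not define improvement or the on-treatment period. It also does not state a denominator; the default in SAP 6.1 is every subject in the treatment group.

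The next sentence adds a second summary: "Descriptive analysis of improvement in these disease-related symptoms will also be presented over the course of the study", for example at each scheduled assessment, by arm. Fatigue is handled separately: "The disease-related symptom of fatigue will be measured by the ECOG performance status", with scores and changes summarised at each timepoint.

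The treatment periods differ by design. Protocol 4.1 says of duvelisib: "Subjects will receive duvelisib continuously for 18 cycles or until disease progression or unacceptable toxicity, whichever comes first". SAP 3.1 likewise has "28-day treatment cycles for up to 18 cycles or until disease progression or unacceptable toxicity", and both documents allow further cycles when the investigator judges that the subject may benefit. For ofatumumab, Protocol 4.1 says: "Administration of ofatumumab will not exceed the 12 doses (within 7 cycles".

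Symptoms are part of the disease response assessments (Protocol 6.3.9 and Table 5). These fall on Day 1 of Cycles 3, 5, 7, 11, 15 and 19 in both arms, and they continue after study drug stops unless there is progression, withdrawal or new anticancer therapy (Protocol 6.5.3.1). SAP 5.3 lists symptom improvement among the exploratory efficacy endpoints.

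**The concern.** Read naturally, the on-treatment proportion counts a subject as improved if the symptom is absent at any assessment during treatment. Such a proportion cannot fall as assessments are added. If the two arms have on-treatment periods of different planned length, the arm treated longer has more chances to record an improvement, even when the drugs relieve symptoms equally well.

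The on-treatment restriction also discards, in the ofatumumab arm only, the assessments planned after Cycle 7. Those are the assessments that would put the arms on the same footing.

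What is at stake is how one descriptive figure is read. A reader who sees two percentages side by side will take the difference as symptom benefit, when part of it may come from the schedule.

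**Working it through.** **Plan's own figure.** None exists for this endpoint: the documents give no rate, sample size or power for symptom improvement. The PFS medians in SAP 3.2 are borrowed below as exit rates. The PFS power stated with them reproduces: |ln 0.6| × √185 / 2 − 1.960 = 1.514, a power of 93.5% against the stated figure of approximately 93%.

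**Looks per arm.** Cycle 1 lasts 21 days and later cycles 28 days (SAP 3.1), so Day 1 of Cycle k falls 21 + 28(k − 2) days after the start.

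- Cycles 3, 5, 7, 11, 15 and 19: days 49, 105, 161, 273, 385 and 497.
- Ofatumumab: 3 scheduled on-treatment looks (Cycles 3, 5, 7).
- Duvelisib: 6 through Cycle 19 Day 1, or 5 if that visit is not counted as on treatment; more if treatment continues.
- Ratio of the planned windows: 497 / 161 = 3.1.
- Adding the 30-day tail used for adverse events in SAP 7.3.1 takes ofatumumab to day 191, still before Cycle 11 (day 273), so it adds no scheduled look.

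**No early exit.** Let p be the chance of a first improvement at each visit, equal in both arms and independent across visits. This is an assumption; the documents give no value. P(ever improved) = 1 − (1 − p)^k for k looks.

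| p | 3 looks | 5 looks | 6 looks | 6 minus 3 |
|---|---|---|---|---|
| 5% | 14.3% | 22.6% | 26.5% | 12.2 |
| 10% | 27.1% | 41.0% | 46.9% | 19.8 |
| 20% | 48.8% | 67.2% | 73.8% | 25.0 |
| 30% | 65.7% | 83.2% | 88.2% | 22.5 |
| 50% | 87.5% | 96.9% | 98.4% | 10.9 |

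The artefact is 11 to 25 points with six looks. With five it is 8 points (22.6 − 14.3) to 18 points (67.2 − 48.8).

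**Equal exit in both arms.** Let treatment end at an exponential rate with median m, the same in each arm: S(t) = exp(−ln 2 × t / m). P(ever improved) is the sum over visits j of S(t_j) × p(1 − p)^(j−1), over 3 visits for ofatumumab and 6 for duvelisib. The values of m are the plan's PFS medians, 9 and 15 months. Differences are taken before rounding.

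| p | m = 9: 3 vs 6 looks | Difference | m = 15: 3 vs 6 looks | Difference |
|---|---|---|---|---|
| 5% | 11.1% vs 15.8% | 4.8 | 12.2% vs 19.1% | 6.9 |
| 10% | 21.1% vs 28.9% | 7.8 | 23.3% vs 34.6% | 11.3 |
| 20% | 38.5% vs 48.5% | 10.1 | 42.2% vs 56.6% | 14.4 |
| 30% | 52.4% vs 61.7% | 9.3 | 57.3% vs 70.5% | 13.2 |
| 50% | 71.7% vs 76.4% | 4.8 | 77.5% vs 84.1% | 6.6 |

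The expected numbers of on-treatment looks are 2.32 vs 3.48 (m = 9) and 2.56 vs 4.25 (m = 15). The artefact is about 5 to 14 points.

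**Early improvement.** If a share q of all first improvements comes after Cycle 7 and the overall improved proportion is R, the gap is R × q. For illustration, R = 60% and q = 10% give 6 points; q = 0 gives none.

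**Common window.** Through Cycle 7 Day 1 both arms have 3 scheduled looks, and the difference is 0 under equal p and equal exit.

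**The case against.** The strongest reply is that the same paragraph already supplies the remedy. The by-assessment summary runs over the study, the schedule is identical in both arms, and subjects who stop drug without progression stay on it. A same-time comparison at Cycles 3, 5 and 7 is therefore planned, and the SAP does not rank the two summaries. This stands as a substantial mitigation. It does not make the on-treatment proportion itself comparable between arms.

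Second, the endpoint is exploratory, no test is specified for it, and it lies outside the PFS, ORR and OS sequence in SAP 6.3. That also stands. A reader might infer a threat to type I error or to a confirmatory claim; the documents give no basis for either.

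Third, a reader might take it that duvelisib subjects generally receive 18 or more cycles. The documents set 18 as a planned maximum subject to progression and toxicity, with continuation optional. Under the plan's own 15-month median, only about 47% would be event-free at Cycle 19 Day 1: exp(−ln 2 × 16.33 / 15) = 0.470.

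Fourth, a reader might quote 20 to 25 points as the expected bias. That needs no early exit, independence between visits, and a constant chance of improvement out to week 71, none of which comes from the documents. The only timing evidence points to early benefit. In the Phase 1 study the median time to response was 1.9 months (Protocol 1.3.2.2), and the 12 partial responses at 25 mg BID or below came after 2, 4 or 6 cycles (6, 4 and 2 subjects; Protocol 1.5). Response is not symptom relief, but this is reason to keep near zero in the range.

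Finally, the direction is a tendency. If more duvelisib than ofatumumab subjects stopped treatment before Cycle 7, the advantage could be offset.

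**Conclusion.** The point holds, and it is minor. Followed as written, the on-treatment proportion for fever, weight loss and night sweats compares the arms over windows of different planned length, up to 5 or 6 or more scheduled looks against 3, and so tends to favour duvelisib without any true difference.

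The direction follows from the documents if improvement means improved at any on-treatment assessment, which is the natural reading but is not defined. The size does not follow from them. It is 11 to 25 points with no early exit, about 5 to 14 points with equal exit at medians of 9 to 15 months, and near zero if first improvements occur by Cycle 7. All of these rest on an assumed equal per-visit chance; the first two take it as 5 to 50%, constant and independent across visits.

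The problem is confined to this one proportion. Fatigue, the by-assessment summary and the formally tested endpoints are untouched.

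**What to change.** Replace the on-treatment proportion in SAP 7.2.3.1 with the proportion improved at any scheduled assessment through Cycle 7 Day 1 in both arms, among randomized subjects with the symptom at baseline, whether or not study drug has stopped. Count as not improved any subject with no improvement recorded before progression, new anticancer therapy, death or dropout. That rule is needed because Protocol 6.3.9 ends these assessments at progression or new therapy. Restricting to subjects with the symptom at baseline settles the denominator, since the others cannot improve. Keep the by-assessment summary for later visits.

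The cost is one SAP sentence and no new data. SAP 7.3.1 already uses a common window for some adverse event tables: onset within 24 weeks of first dose, or 168 days, close to Cycle 7 Day 1 at day 161. The downside is that improvements first seen after Cycle 7 will appear only in the by-assessment summary.
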